Variables	For the evaluations of the mentioned clinical outcomes the following parameters will be captured: Part 1: 
○ Demographic data (age, gender, weight, body surface)○ Date of first diagnosis○ Stage and risk rating (IMDC) at first diagnosis and at start of 1L○ Assessments and results of PD-L1 expression○ Non-medicinal pre-treatments (primary operation (OP), cytoreductive nephrectomy, radiotherapy)○ Medicinal pre-treatments (adjuvant, neoadjuvant)○ Location of administration and performing medical discipline○ Administered drugs / protocols in 1L○ If applicable: Reason for ineligibility of ICI○ Dates of administrations for i.v. drugs in 1L○ Duration of 1L treatment○ Dosages per administration○ Dose modifications or drug administration cancelling or interim / permanent discontinuations of single drugs / complete therapy in 1L○ Reasons for modifications, cancelling of single administrations and discontinuations in 1L○ Supportive drugs prescribed during 1L○ Date of first response and best response to 1L incl. date and mode of assessment

- Assessment of first and best response in 1L
- Date of tumor progression
- Reasons for end of 1L
- Subsequent therapies (2L and higher) with drugs/protocol and dates for start / end
- Concomitant diseases and therapeutic medications

Part 2:

If patients will qualify for part 1 and part 2 (completion of 1L and follow-up of at least 3 months after completion), the documented data from part 1 will be transferred to part 2 automatically, so that only additional parameters must be filled in. If patients are newly documented in part 2, all of the parameters have to be documented.

- Demographic data (age, gender, weight, body surface)
- Date of first diagnosis
- Stage and risk rating (IMDC) at first diagnosis and at start of 1L
- Assessments and results of PD-L1 expression as TPS
- Non-medicinal pre-treatments (primary OP, cytoreductive nephrectomy, radiotherapy)
- Medicinal pre-treatments (adjuvant, neoadjuvant)
- Location of administration and performing medical discipline
- Administered drugs / protocols in 1L
- If applicable: Reason for ineligibility of ICI
- Dates of administrations for i.v. drugs in 1L
- Dosages per administration
- Dose modifications or drug administration cancelling or interim /permanent discontinuations of single drugs / complete therapy in 1L
- Reasons for modifications, cancelling of single administrations and discontinuations in 1L

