Study Size	Based on public data the population of patients with aRCC and an indication for a 1L therapy is around $n = 4.500 - 5.000$ patients per year (Robert Koch Institute 2020). In the period of 01 January 2020 – 31 December 2021, which is the main period of interest in the study for completing or starting 1L therapies, the total population of patients with aRCC would be around $n = 9.000 - 10.000$ patients. To estimate the needed number of patients in the study to reach adequate representation across Germany, the following common formula is used $n = \frac{z^2 \pi(1 - \pi)N}{z^2 \pi(1 - \pi) + E^2(N - 1)}$ 
N = population of patients with aRCC and indication for 1L = 10.000 patients in 24 months Π = 0,5 (consensus, if attribute is unknown before study) E = margin of error = 5% = 0,05 Z = 1,96 (for confidence interval of 95%)
 
Based on these assumptions (PFS of 1L therapies included in guidelines was 8.4 – 15.1 months in clinical studies) the number of patients needed for representative statement regarding the primary objective (= PFS rates at defined time points under real world conditions) is at least $n = 370$. With a buffer of around 10% the sample size in the study should be $n = 400$ patients with aRCC and 1L therapies in the period from 01 January 2020 – 31 December 2021. Based on published data for PFS it could be

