7. RATIONALE AND BACKGROUND

In clinical trials, patients are treated strictly according to a study protocol and show sometimes different risk factors, fewer comorbidities or a lower age than patients under standard care conditions. However, there is limited larger data collections on current therapy behavior in the 1L of patients with RCC, who are treated under standard care conditions in Germany.

The special interest of this retrospective Medical Chart Review project is to obtain in a Part 1 more precise data for the distribution of different 1L therapies of patients with aRCC, which have started within 01 January 2020 – 31 December 2021 and are representative for Germany. In Part 2 the effectiveness, sequences as well as the frequencies and handling of intolerabilities of combination therapies (ICI + TKI or ICI + ICI) in 1L aRCC will be analyzed by capturing data of patients, who completed a 1L in 01 January 2020 – 31 December 2021 with a follow up period of at least 3 months after completion. All data describe also the current therapy behavior and the resulting clinical effectiveness of the individual therapy protocols used in the 1L. These data allow the transferability of the results from clinical studies to standard care as well as the specific handling of intolerabilities. Particular emphasis is placed on analyses of this handling of intolerabilities during combination therapies with ICI + TKI or ICI + ICI. Information about current processes in decision findings regarding dose modifications or interruptions or interim / permanent discontinuations of one or both drugs can help to unify processes and to develop standard recommendations for daily care situations. Another point of the data analysis lies in the area of the medical disciplines and institutions that initiate and carry out 1L therapies for aRCC under standard care conditions. Questions about the different therapeutic behavior between urologists and medical oncologists, between practices and hospitals and between different regions in Germany are of particular relevance.

[figure not shown]
In conclusion, the rationale of this study is more clarity in the effectiveness of different 1L therapies, more clarity in the accordance of 1L therapies to national guidelines and more clarity in the handling of intolerabilities or other situations where dose modifications or discontinuation of treatment occurs

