8.1. Primary Research Questions

Based on the above background, there are currently a number of unanswered questions for health services research:

- How is the effectiveness, defined as measurement of beneficial effects under “real world” clinical settings, (e.g. progression-free survival, overall survival and best response) of TKI and/or ICI as 1L in patients with aRCC?
- How are patients with aRCC treated in 1L under daily care conditions in Germany in general and in accordance to medical specialities (urology and medical oncology) and treatment settings (hospitals vs office-based practices)?
- Are all patients assigned to individual risk ratings under standard daily care conditions according to a scale developed by the IMDC before start of a 1L?
- How are patients treated in 1L in different risk rating groups and how is the adherence to national/international guidelines?
- What kind of previous and subsequent therapies are administered before and after 1L?
- How often are evaluations for PD-L1 expression performed before start of 1L and how many patients are positive (TPS $\geq 1\%$) or negative?

- How long are patients treated with TKI + ICI and ICI + ICI in 1L in general and in relation to specific therapies like avelumab + axitinib?
- How frequent are dose modifications and early discontinuations and what are the reasons?
- Are there differences in the handling of modifications among medical disciplines?

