8.2. Study Objectives

To answer these questions the following objectives are derived:

Primary Objective(s):

- Progression-free survival (PFS) for 1L therapies, expressed as median and as rates at timepoints of 6, 9, 12 and 18 months after start of 1L

Secondary Objectives:

- Overall survival (OS) of 1L therapies, expressed as median and rates at timepoints of 12 and 18 months after start of 1L therapy
- Best response in 1L overall and in dependence of administered drug regimen
- Progression-free survival of 1L therapies in dependence of specific drug regimen
- Pre- and post-treatments (i.e. surgery, radiotherapy, medicinal therapies) before/after TKI + ICI and ICI + ICI in 1L
- Duration of response (DoR) in 1L overall and in dependence of administered drug regimen (TKI + ICI or ICI + ICI)
- Frequency of dose modifications and temporary/permanent discontinuations of 1L therapies and their reasons
- Proportions of modifications by dose reduction compared to cancelling single applications
- Effectiveness (PFS, OS and best response) of administered 1L therapies under real world conditions by medical specialty (urology, medical oncology) and setting (practice, hospital)

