9.1.1. Inclusion criteria

Patients must meet all of the following inclusion criteria to be eligible for inclusion in the study:

Part 1 and 2:

- Patients aged ≥ 18 years old
- Patients with histologically/cytologically confirmed renal cell carcinoma (ICD-10 C64)
- Full medical information regarding all treatments before, during and after 1L should be available.

Specific inclusion criteria only for Part 1:

- Patients with locally advanced or metastatic disease and a start of any systemic 1L therapy against RCC between 01 January 2020 and 31 December 2021

Specific inclusion criteria only for Part 2:

- Patients with locally advanced or metastatic disease, who were treated with a combination of ICI + TKI or ICI + ICI as 1L therapy against RCC and who had a completion of this therapy between 01 January 2020 - 31 December 2021 with a follow-up period of at least 3 months after completion of the 1L.

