9.4. Study size

Based on public data the population of patients with aRCC and an indication for a 1L therapy is around $n = 4.500 - 5.000$ patients per year ([Robert Koch Institute 2020](#)). In the period of 01 January 2020 – 31 December 2021, which is the main period of interest in the study for completing or starting 1L therapies, the total population of patients with aRCC would be around $n = 9.000 - 10.000$ patients. To estimate the needed number of patients in the study to reach adequate representation across Germany, the following common formula is used

$$n = \frac{z^2 \pi(1 - \pi)N}{z^2 \pi(1 - \pi) + E^2(N - 1)}$$

N = population of patients with aRCC and indication for 1L = 10.000 patients in 24 months

$\Pi = 0,5$ (consensus, if attribute is unknown before study)

E = margin of error = 5% = 0,05

$Z = 1,96$ (for confidence interval of 95%)

Based on these assumptions (PFS of 1L therapies included in guidelines was 8.4 – 151 months in clinical studies) the number of patients needed for representative statement regarding the primary objective (= PFS rates at defined time points under real world conditions) is at least $n = 370$. With a buffer of around 10% the sample size in the study should be $n = 400$ patients with aRCC and 1L therapies in the period from 01 January 2020 – 31 December 2021. Based on published data for PFS it could be assumed for part 2, that also the number of patients with combination therapies in part 2 ($n = 300$) will grant a representative statement to all research questions. Based on information of urological and oncological experts as well as own data of the GermanOncology *¹ network (see below), the following assumptions could be set:

- Number of patients with new 1L in urological practices (per practice 1- 3 urologists) = 4 - 6 per year
 - Number of patients with new 1L in period of 24 months = 8 - 12
- Number of patients with new 1L in oncological practices (per practice 2- 4 oncologists) = 4 - 6 per year
 - Number of patients with new 1L in period of 24 months = 8 - 12
- Number of patients with new 1L in hospitals with urological focus = 8 - 12 per year
 - Number of patients with new 1L in period of 24 months = 16 – 24
- Proportion of 1L therapies in urological and oncological practices: 50% : 50%
- Proportion of patients treated with 1L in practices and hospitals (as most of therapies are oral therapies): 65% : 35%

Based on the assumptions the needed number of sites are at least:

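### Part 2 admits only combination patients whose first-line therapy has ended, so it cannot give representative PFS or treatment duration for the combinations; 9.6 should take these from Part 1

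*Combined protocol and SAP*

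**What the plan says.** Section 9.1.1 defines the two parts differently. Part 1 takes patients who started any systemic 1L in 2020–2021. Part 2 takes patients on ICI + TKI or ICI + ICI "who had a completion of this therapy between 01 January 2020 - 31 December 2021 with a follow-up period of at least 3 months" after the end of 1L. It sets no limit on the start date.

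Section 7 divides the purposes. Part 1 is "to obtain in a Part 1 more precise data for the distribution of different 1L therapies of patients with aRCC". For the combinations the text reads: "In Part 2 the effectiveness, sequences as well as the frequencies and handling of intolerabilities of combination therapies". Section 9.4 and the abstract then say that the 300 patients of Part 2 "will grant a representative statement to all research questions". Those questions include effectiveness and, in 8.1, "How long are patients treated with TKI + ICI and ICI + ICI in 1L in general". Section 8.2 adds as a secondary objective "Progression-free survival of 1L therapies in dependence of specific drug regimen".

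The 370 (400 with buffer) is tied to "the primary objective (= PFS rates at defined time points under real world conditions" and to patients with 1L in the 2020–2021 period. Section 9.6 analyses all evaluable patients, and the abstract's Data Analysis row uses the total group. Neither says which part supplies which estimate. Some patients enter through Part 2 alone: "If patients are newly documented in part 2, all of the parameters have to be documented". Section 9.8 lists only data availability and missing data as limitations.

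**The concern.** Table 2 (9.2) lists progression and death among the reasons for the end of 1L. A rule that requires 1L to have ended by a fixed date therefore selects on the outcome. A combination patient who does well and is still on treatment at 31 December 2021 does not contribute censored time to Part 2; the patient is not in it. Patients eligible only for Part 2 are selected the other way: they started before 2020 and were still on 1L on 1 January 2020.

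If section 7 is followed, PFS and treatment duration for the combinations would describe patients who stopped in a calendar window, not patients who start these regimens. Two regimens with the same true PFS but different uptake could look different, and a comparison with the pivotal figures in section 8 could mislead. How often all 1L therapy is ended cannot be estimated in a sample where everyone has ended it.

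**Working it through.** **Plan's own figure.** n = z²π(1−π)N / [z²π(1−π) + E²(N−1)] with z = 1.96, π = 0.5, N = 10,000, E = 0.05 gives 369.98, so 370 reproduces. Part 2's 300 has no calculation of its own. A half-width of 5.6 points at n = 300 says nothing about selection.

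**Inputs.** Median PFS 15.1 and 23.9 months is the pivotal range in section 8, which is for ICI + TKI only; no figure is given for ICI + ICI. Assumed: exponential times; uniform starts; first use a months before January 2020; a share q of 1L ends that are neither progression nor death, 0–40%.

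**Step 1: who is missing from Part 2.** This needs no history before 2020. Among uniform 2020–2021 starters, the share still on 1L at month 24 is (1 − e^(−24H)) / (24H), with H = ln 2 / [median × (1 − q)].

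| Median | q = 0 | q = 0.2 | q = 0.4 |
|---|---|---|---|
| 15.1 | 61% | 54% | 46% |
| 23.9 | 72% | 67% | 59% |

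**Step 2: what Part 2 would show when every end of 1L is a PFS event.** The density of admitted times is proportional to λe^(−λt) × w(t), where λ = ln 2 / median. The admissible start interval w(t) is 24 for t ≤ a and 24 + a − t for a < t ≤ 24 + a.

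| First use | True 15.1 appears as | True 23.9 appears as |
|---|---|---|
| Jan 2020 (a = 0) | 5.4 | 6.0 |
| Jan 2019 (a = 12) | 8.6 | 9.7 |
| Jan 2018 (a = 24) | 11.1 | 13.3 |
| Jan 2015 (a = 60) | 14.3 | 19.8 |
| Constant use over many years | 15.1 | 23.9 |

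At a true median of 15.1 and first use in January 2019, 12-month PFS is 35% in Part 2 against a true 58%.

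**Step 3: ends of 1L that are not PFS events.** For first use in January 2019 and median 15.1, simulation gives a Part 2 median PFS of 9.8 (q = 0.2) or 11.4 (q = 0.4). Median duration is 7.9 instead of 12.1, or 6.9 instead of 9.1. The shortening is 35% and 24% for both measures.

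**Step 4: pooling Part 2-only patients into the total group.** Let f be the share of Part 2 who started before 2020, with 12-month PFS So. Of the other 300(1 − f), some are already among Part 1's 400 and the shortfall m is newly documented, with 12-month PFS Si. The pooled rate is (400·S1 + 300f·So + m·Si) / (400 + 300f + m). Assume 50–80% combinations in Part 1, median 15.1, and median 8.4 for other 1L (the lower figure in the abstract's study-size text).
- First use January 2019, q = 0, 50% combinations: f = 0.395, so 182 patients are needed from 2020–2021 starters and Part 1 holds about 79, giving m ≈ 103. S1 = 0.474, So = 0.626, Si = 0.17. The pooled rate is 0.453, a change of −2.1 points.
- First use January 2015, q = 0, 80% combinations: m = 0, and the rate moves from 0.535 to 0.626, about +9 points.

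Across first use from 2019 to 2015 and q from 0 to 0.4, the change runs from about −2 to +9 points.

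**The case against.** Four objections carry weight.

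*The primary endpoint looks safe.* The 400 are start-defined patients sized for PFS rates, and the abstract lists duration of 1L among the Part 1 variables but not the Part 2 variables. A reader might infer from the selection that the primary PFS is invalid. The documents do not support that: the natural reading takes it from Part 1, which also holds the combination patients who started in 2020–2021. What is missing is the statement that it does.

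*The bias depends on uptake.* This stands. With long constant use, sampling by completion recovers the true median, and with falling use the bias can reverse. The documents give no uptake dates. The ICI + TKI pivotal reports they cite date from 2019–2021, which makes long stable use doubtful but does not settle it.

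*Discontinuation.* A reader might infer that Part 2 would report 100% permanent discontinuation. That does not follow. The abstract's definition is broad, but Table 2 gives discontinuation its own reasons, without progression, and records reasons for the end of 1L in a separate row. Whether an end for progression counts as a permanent discontinuation is unclear. Setting a 12-month share in a start-defined cohort against an all-time share in Part 2 would not measure selection either.

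*The analysis detail is deferred.* Section 9.6 leaves methods to a separate SAP, so silence there is weaker evidence. But the entry rule, the purpose of Part 2 and the representativeness claim are protocol content, and a SAP cannot put back patients never sampled into Part 2.

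**Conclusion.** The point holds for the secondary, combination-specific estimates and should be fixed. Entry to Part 2 depends on the outcome, the protocol assigns combination effectiveness to it, and nothing confines PFS or duration to Part 1.

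The mechanism follows from the criteria; the size does not. The 46–61% missing rests on exponential times, uniform starts and a median of 15.1. The apparent medians of 5.4 to 14.3 months also rest on an assumed date of first use and on every end of 1L being a PFS event. Applying these inputs to ICI + ICI is a further assumption.

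A reader might also infer that pooling Part 2-only patients would inflate the overall PFS. Neither sign nor size is established, since both depend on uptake and on the overlap between the parts. The direction of any bias in OS is likewise open, partly because the 3-month criterion does not say how early deaths are treated.

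**What to change.** 1. In 9.6, state that PFS, OS, DoR, TTP, treatment duration and frequency of permanent discontinuation, overall and by combination regimen, are estimated in the start-defined Part 1 cohort with censoring. State that patients eligible only for Part 2 are not pooled into these estimates.
2. Limit Part 2 to modifications, their handling, reasons and treatment sequences among patients who ended 1L.
3. In 9.4 and the abstract, replace the claim that Part 2 is representative for every research question. In 9.8, list selection on completion and the Part 2 regimen quotas set in 9.1.2.
4. In 9.1.1, clarify how death on 1L, or within 3 months of its end, is treated under the follow-up criterion.

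**Cost.** This is wording only, and it is feasible: the last Part 1 start (31 December 2021) has 9–13 months of potential follow-up at documentation (1 October 2022 to 30 January 2023). The price is precision. For an assumed 200–320 combination patients in Part 1 (50–80% of 400), median 15.1 and censoring at documentation, the Greenwood 95% half-width at 12 months is 6.9–5.4 points. For 300 uncensored patients it is 1.96 × √(0.576 × 0.424 / 300) = 5.6 points. Single regimens will be less precise.

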- Progression-free survival (PFS) for 1L therapies, expressed as median and as rates at timepoints of 6, 9, 12 and 18 months after start of 1L

Secondary Objectives:

- Overall survival (OS) of 1L therapies, expressed as median and rates at timepoints of 12 and 18 months after start of 1L therapy
- Best response in 1L overall and in dependence of administered drug regimen
- Progression-free survival of 1L therapies in dependence of specific drug regimen
- Pre- and post-treatments (i.e. surgery, radiotherapy, medicinal therapies) before/after TKI + ICI and ICI + ICI in 1L
- Duration of response (DoR) in 1L overall and in dependence of administered drug regimen (TKI + ICI or ICI + ICI)
- Frequency of dose modifications and temporary/permanent discontinuations of 1L therapies and their reasons
- Proportions of modifications by dose reduction compared to cancelling single applications
- Effectiveness (PFS, OS and best response) of administered 1L therapies under real world conditions by medical specialty (urology, medical oncology) and setting (practice, hospital)

Study Design	This is a retrospective, non-interventional, observational, multicenter, Medical Chart Review project in patients with aRCC, who received a systemic 1L therapy between 01 January 2020 – 31 December 2021 under daily routine conditions in hospitals or practices in Germany. At timepoint of enrollment of patients, all decisions for specific treatment regimen or investigations were already made under discretion of the physicians and in accordance to the routine clinical practice. The study should describe and analyze in part 1 and part 2 for the the treatment situation from adult patients with aRCC in 1L as well as the clinical
---------------------	--

	
outcomes and handling of intolerabilities from combination therapies in 1L under daily routine in general and in relation to specific therapies.
 
Only data from medical records for running therapies between 01 January 2020 - 31 December 2021 will be captured under conditions of full anonymization. Based on the full anonymization a written informed consent by the patients or an advice by participating doctors an Independent Ethical Committee (IEC) regarding accordance with professional law should not be necessary.

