- Supportive drugs prescribed during 1L
- Date of first response and best response in 1L incl. mode of assessment
- Assessment of first and best response in 1L
- Date of tumor progression
- Reasons for end of 1L
- Subsequent therapies (2L and higher) with drugs/protocol and dates for start / end
- Concomitant diseases and therapeutic medications

Data Sources	Source documents (paper or electronic medical charts) are those, in which patient data of daily care are recorded and documented in individual patient files. The data to be collected in the study will be obtained via a specific programmed eCRF. The data in the eCRF should be consistent with the relevant source documents. Medical records should contain demographic data, medical data, treatments and diagnostic documentations according to common practice. The documentation will be performed under full anonymization, so that a re-identification of single patients will not be possible. Based on this anonymization, queries for explanations or changes of data could not be submitted by the data management. All documented variables will be checked by data manager and/or medical lead of GermanOncology in relation to implausibility, inaccuracies or missing data. If implausibility or inaccuracies or missing data of single patients will be of great relevance for analyses, the data management and/or medical lead have the right to reject patients. For such rejected patients no payment will be triggered.

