9.1.2. Exclusion criteria

Exclusion criteria for part 1 and 2

Patients meeting the following criteria will not be included in the study:

- Patients participating in an interventional clinical study within 30 days before start of 1L

All sites are asked to document all of their patients with the fulfilled inclusion and not fulfilled exclusion criteria, starting with the earliest start (in part 1) and the longest follow-up period (in part 2), respectively. The patients should be treated with the systemic 1L therapy in the site and data should be available in the medical records of the sites. The enrollment will be competitively over all participating sites without a limitation for the single sites. In part 2 quotas for groups with ICI + TKI and ICI + ICI and with the specific therapy avelumab + axitinib or nivolumab + ipilimumab will be set up.

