9.5. Data management

The main purpose of the specific eCRF is to obtain data required by the study protocol in a complete, accurate, legible and timely manner. The data in the eCRF should be consistent with the relevant source documents in the practices and hospitals. The investigator or his/her designee is responsible for ensuring that the data collected in the course of this study are accurate and documented appropriately and completely in all applicable forms. Data will be documented, processed, evaluated, and stored in fully anonymous form in accordance with applicable data protection regulations. The investigator must ensure that the eCRFs and any other associated documents forwarded to the project management contain no mention of any subject names or other personalized information. The data will be entered by the eCRF into a validated database. The project management will be responsible for data processing, in accordance with the Sponsor's data management procedures. The sponsor will receive only full anonymized data or aggregated reports, without any options for re-identification of patients and/or sites. Database lock will occur once quality control and quality assurance procedures and second, that activities of documentation and coding have been completed. The eCRF has a modular structure with separation of contents to build up all sequences and information of treatments from date of first diagnosis up to the present date or death or lost-of-follow-up. Data must be filled in completely and legibly by choosing parameters out of a pre-defined drop-down-list, or in a few cases by writing free text. All corrections will be listed in a history trail with name of corrector and date of correction. Relevant fields are declared as mandatory and must be fulfilled definitively before triggering any payment. As part of the data quality process, all entries in the eCRF will be checked by data manager. In cases of implausibility or incorrectness or inaccuracy or relevant missing data, the data manager together with the medical lead of GermanOncology are allowed to reject patients with a statement of an appropriate reason. Every patient's documentation file is given a randomized code of numbers and letters, automatically generated by an encryption algorithm. As only anonymized data will be sampled, this data handling and storage can be described as "full anonymized" in accordance to the recital 25 of the German and EU General data protection regulation.

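### The Part 2 follow-up condition does not say how deaths during or soon after first-line therapy are treated, so sites can build different cohorts, and Part 2 should not be the source of OS and PFS

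*Combined protocol and SAP*

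**What the plan says.** Section 9.1.1 limits Part 2 to patients on ICI + TKI or ICI + ICI whose 1L was completed between 1 January 2020 and 31 December 2021, "with a follow-up period of at least 3 months after completion of the 1L". The Abstract (Population) and Section 7 repeat the condition. The Abstract (Variables) uses it to decide which Part 1 patients pass into Part 2: "completion of 1L and follow-up of at least 3 months after completion". None of these places defines completion or follow-up, or mentions death.

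Other text bears on the reading:
- Section 9.1.1 also asks, for both parts: "Full medical information regarding all treatments before, during and after 1L should be available".
- Section 9.1.2 tells sites to document all eligible patients, in Part 2 beginning with "the longest follow-up period (in part 2"). Enrolment is competitive, with quotas by regimen.
- The Part 2 variable list in the Abstract includes "Reasons for end of 1L", and Tab. 2 (Section 9.2) offers death as one of the answers.
- Section 9.5 has the eCRF follow the course "up to the present date or death or lost-of-follow-up".
- The Abstract (Study Design) says: "Only data from medical records for running therapies between 01 January 2020 - 31 December 2021 will be captured".

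Section 7 assigns the effectiveness of combination therapy to Part 2, and Section 9.4 treats its 300 patients as representative for every research question. Part 1 is entered by start of 1L and has no follow-up condition.

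**The concern.** A person abstracting charts has to decide whether someone who died on 1L, or six weeks after it, has the required 3 months. The protocol gives no answer, and up to 40 sites may decide differently. If such patients are left out, death as a reason for ending combination 1L is empty in Part 2 by construction, and OS there is conditional on surviving at least 3 months beyond the end of 1L. That would sit badly with the use of Part 2 for effectiveness.

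The documentation order can add to this. If follow-up means observed time, long survivors are entered first. This matters only if a quota or the target of 300 fills before a site's list is exhausted.

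The choice is hard to trace afterwards. A patient left out of Part 2 leaves no Part 2 record, and because of anonymisation "queries for explanations or changes of data could not be submitted by the data management".

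**Working it through.** **Plan's own figure.** Section 9.4 uses n = z²π(1−π)N / [z²π(1−π) + E²(N−1)]. With z = 1.96, π = 0.5, E = 0.05 and N = 10,000 this gives 369.98, so the stated 370 is reproduced. Solved for the margin, E = 1.96·√[0.25/n · (N−n)/(N−1)], which is 5.57 points at n = 300.

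**Elapsed-time reading.** The latest eligible completion is 31 December 2021 and data collection starts 1 October 2022 (Section 6). The gap is 274 days, or 9.0 months, and 13.0 months to the end of collection on 30 January 2023. Every completer exceeds 3 months, so the rule excludes nobody.

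If the Study Design sentence were a data cut-off at 31 December 2021, the rule would remove completions after 30 September 2021, which is 92 of 731 days (12.6%). That conflicts with Section 9.5, which follows patients to the present date.

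**Observed-time reading.** A death on 1L leaves 0 months afterwards, and a death within 3 months leaves fewer than 3. Both are excluded. Patients lost within 3 months also go, although the full-information criterion may already remove some of them.

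**Three months or until death.** Deaths stay in and only patients lost early go out.

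**Size on the observed reading.** The survival inputs are assumptions. Starts are uniform from January 2019 or January 2017. Time on 1L is exponential with median 15.1 months, the lower end of the pivotal PFS range in Section 8. Survival after 1L is exponential with median 12 months. Of 1L courses, 0, 10 or 20% end in death. End of 1L stands in for the PFS event, which is a simplification. The share excluded is 1 − (1−p)·2^(−3/12) = 15.9, 24.3 and 32.7% for p = 0, 0.1 and 0.2.

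12-month OS (%), by simulation with 3 million patients per case:

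| Starts from | Deaths on 1L | All starters | Completers 2020-21 | Completers with 3 months observed | Effect of rule | Net error with rule | Net error without rule |
|---|---|---|---|---|---|---|---|
| 2019 | 0% | 87.2 | 80.4 | 87.8 | +7.4 | +0.6 | −6.8 |
| 2019 | 10% | 84.3 | 75.9 | 87.9 | +12.0 | +3.5 | −8.4 |
| 2019 | 20% | 81.3 | 71.2 | 87.8 | +16.6 | +6.5 | −10.1 |
| 2017 | 0% | 87.3 | 85.6 | 91.1 | +5.5 | +3.8 | −1.6 |
| 2017 | 10% | 84.3 | 82.3 | 91.1 | +8.8 | +6.8 | −2.1 |
| 2017 | 20% | 81.3 | 78.9 | 91.0 | +12.1 | +9.7 | −2.4 |

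Differences come from unrounded values. A repeat run with another seed agreed within about 0.1 point. A cohort indexed at 1L start in 2020-21 returned the all-starter value in every case.

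**Wider grid.** The grid has 108 cells: median time on 1L 8.4, 15.1 or 23.9 months; median survival after 1L 9, 12 or 18 months; deaths on 1L 0, 10 or 20%; starts from 2019 or 2017; gamma frailty variance 0 or 0.5.
- Effect of the rule against completers: +3.3 to +21.0 points.
- Net error with the rule: −4.2 to +15.9 points, positive in 94 cells and beyond the 5.6-point margin in 45.
- Net error without the rule: −19.0 to −0.2 points. Its absolute size is larger than with the rule in 60 cells (44 of 54 with starts from 2019, 16 of 54 from 2017).

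**PFS.** The rule changes 12-month PFS by 0 when time on 1L and later survival are independent, and by at most about +3 points with frailty or with deaths on 1L concentrated early. The completion window, by contrast, takes 12-month PFS from 57.6% to 34.9% (starts from 2019) or 52.1% (from 2017).

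**The case against.** The strongest reply is that the damaging reading is only one of three, and that the text leans away from it. Tab. 2 allows death as a reason for ending 1L, Section 9.5 ends the record at death, and longest follow-up in Section 9.1.2 can simply mean earliest completion first, parallel to earliest start in Part 1. The reading of 3 months or until death fits these places and gives the rule a sensible purpose. This stands. A reader might infer that Part 2 does exclude early deaths, or that this is what sites would most likely do; the documents support neither.

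Second, the 3-month clause is not solely responsible for deaths on 1L. Whether such a death counts as completion is a prior question that is equally open. With no deaths on 1L, the base-case net error is +0.6 or +3.8 points, both under the 5.6-point margin. This also stands.

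Third, one might infer that no SAP could repair the problem. That goes too far. Combination patients who started 1L in 2020-21 are eligible for Part 1 whatever their follow-up, Section 9.6 leaves methods to the SAP, and no text says that OS comes from Part 2 alone. Only patients who started before 2020 and were left out of Part 2 are beyond recovery.

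What the reply does not remove is that the wording lets sites differ, and that Section 7 gives combination effectiveness to a cohort selected by completion date, by this condition and by length of follow-up.

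**Conclusion.** The point holds as an ambiguity with a material consequence on one reading, and it should be fixed. The missing definitions and the 9.0-month minimum are certain. On the observed reading, the empty death category and the upward shift in OS against the same completers follow by construction. The size of that shift, about 5 to 17 points at 12 months in the base cases, rests on assumed survival inputs.

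A reader might infer that Part 2 OS is therefore overstated by that amount. It is not: against all 1L starters the net error is smaller in the base cases and of uncertain sign across the grid, because entry by completion date works the other way. Nor does the condition threaten the primary outcome to any extent. The larger PFS distortion comes from the completion window, and both are avoided by estimating from the Part 1 cohort.

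**What to change.** Make three changes together.

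1. In Section 9.1.1 and the matching Abstract text (Population, Variables), state that patients who die during 1L or within 3 months after it are eligible for Part 2, that death on 1L counts as completion, and that the 3 months are potential follow-up to a stated data date. Reconcile the Study Design sentence in the Abstract with Section 9.5 on that date.
2. In Section 9.1.2, replace the longest-follow-up-first order for Part 2 with documentation of all eligible patients, or a random sample of the site's list if a quota fills.
3. Take OS and PFS, overall and by combination regimen, from the Part 1 cohort indexed at 1L start. Add date of death or last contact to Tab. 2, which names neither. Keep Part 2 for treatment handling, modifications, discontinuation reasons and sequences, and amend its purpose in Section 7.

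The third change is essential, since the first alone gave a larger absolute OS error in 60 of 108 cells.

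The cost is protocol wording, one eCRF field and some precision. Regimen estimates lose the Part 2 quotas. If combinations make up 50, 65 or 80% of the 400 Part 1 patients (an assumption), n is 200, 260 or 320 and the margin 6.9, 6.0 or 5.4 points, against 5.6 for 300 in Part 2. A regimen with 100 patients has 9.8. Follow-up is also shorter: a patient starting on 31 December 2021 has 13.0 months by 30 January 2023, and only 9.0 if abstracted on 1 October 2022. Late starters should therefore be abstracted late, and 18-month rates will need censoring.
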